### **b. Power analysis (All experiments)**

All experiments in this protocol are powered based on the primary outcome, which relates to modulating FC within the targeted networks.

A power analysis was conducted on our preliminary data using G\*Power v3.1. We used a repeated-measures ANOVA model with FC changes between the hippocampus and the precuneus/medial occipital cortex as my dependent variable. The precuneus/medial occipital cortex was used because these regions showed the most robust response to stimulation in Wang et al., (2014). Based on these data (Mean Difference = 0.16, Pooled Standard Deviation = 0.21, Cohen's  $d = 0.75$ ), and assuming power of 0.80 and  $\alpha = 0.05$ , 26 right-handed healthy participants between 18 and 40 years of age will be needed (13 per group) for each experiment (104 total). To account for attrition (estimated ~15%), we will request an accrual ceiling of 122.

There were no preliminary data to conduct a power analysis for stimulation involving the striatal network. Thus, we propose to have 13 analyzable subjects in the M1 group, the same number as in the parietal group from Experiments 1 and 3. We also plan to obtain 13 subjects in the control group, resulting in 26 analyzable healthy subjects (13 per group).

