#### c. Resting-State vs. Task-Based Connectivity

The results of Wang et al. (2014) and data from our laboratory show that rTMS can enhance rsFC within a targeted network. However, it is unknown whether the same is true of tbFC. Because tbFC may be a better measure of stimulation-induced changes, we will include this measurement in our experiments and compare the results to rsFC.

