**Contingency for Experiments 3 and 4 if we are unable to inhibit each network.** Because targeted inhibition of the hippocampal and striatal network with cTBS has not been demonstrated, it is possible that cTBS may not yield the expected inhibitory effects in Experiments 3 and 4. Thus, we will examine the results from the first three subjects receiving active stimulation in Experiments 3 and 4 and if there is no clear decrease of FC in the targeted network, we will run a cohort of 3 subjects using 1-Hz rTMS. We will proceed with the stimulation type that demonstrates the most reliable inhibitory effect.

*1-Hz Stimulation.* Stimulation will be delivered at 115% of the motor evoked potential threshold at 1-Hz continuously for 16 minutes (similar to Chen et al., 1997).

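### Section 10.b says every experiment is powered on its primary outcome, but its one planning effect informs only resting-state FC in Experiment 1

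*Combined protocol and SAP*

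**What the plan says.** Section 10.b is headed as covering all experiments and opens: "All experiments in this protocol are powered based on the primary outcome, which relates to modulating FC within the targeted networks". It then gives one calculation. The model is described as follows: "We used a repeated-measures ANOVA model". The variable is "FC changes between the hippocampus and the precuneus/medial occipital cortex as my dependent variable", and the inputs are "Mean Difference = 0.16, Pooled Standard Deviation = 0.21", with Cohen's d given as 0.75 and alpha as 0.05. On these inputs, "assuming power of 0.80", the section arrives at 26 participants (13 per group) and applies that number to each experiment, 104 in total.

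The next paragraph of 10.b says: "There were no preliminary data to conduct a power analysis for stimulation involving the striatal network". It therefore takes 13 per group for the M1 experiments to match the parietal ones.

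Three other places bear on what the calculation covers:

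- Section 9.a makes both resting-state FC (rsFC) and task-based FC (tbFC) in the targeted network primary, and section 2.a names both in each of the four primary aims.
- Section 1.c says the laboratory's data show enhancement of rsFC, and adds: "However, it is unknown whether the same is true of tbFC".
- Section 4.d.iv, on Experiments 3 and 4, says: "Because targeted inhibition of the hippocampal and striatal network with cTBS has not been demonstrated". It provides an early look at three actively stimulated participants and a possible change to 1-Hz stimulation.

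**The concern.** A power statement is a claim about particular outcomes. Here the claim covers four experiments and two FC measures, while the evidence behind it is one uncontrolled pre-to-post change, at one set of regions, for one site and one direction of stimulation. If the claim stands, a non-significant result in Experiments 2 to 4, or on tbFC in any experiment, would be set against a stated 80% power that nothing in the protocol supports. Section 2 says the results will inform later trials in patients, so the weight a reader gives to a null result matters.

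**Working it through.** **1. What the planning effect covers.** Section 1.b describes the pilot: nine people, stimulation through the parietal site, enhancement of the hippocampal network, no vertex group reported. Section 1.c places the laboratory's data in rsFC. Section 10.b names neither the frequency nor the FC type. The 20-Hz setting is inferred from section 1.a, which describes the technique the pilot replicates.

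| Experiment | Stimulation, network | rsFC: planning effect? | tbFC: planning effect? |
|---|---|---|---|
| 1 | 20-Hz, hippocampal | Yes (pilot) | None; unknown per 1.c |
| 2 | 20-Hz, striatal | None; conceded in 10.b | None |
| 3 | Inhibitory, hippocampal | None; cTBS inhibition not demonstrated per 4.d.iv, and no effect size given for 1-Hz | None |
| 4 | Inhibitory, striatal | None; conceded in 10.b | None |

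The concession in 10.b concerns the striatal network only. It does not mention Experiment 3 or tbFC.

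**2. The plan's own 26.** The section does not state the number of measurements, their correlation, the tested term or the sidedness. Two sets of unstated settings give the plan's figure:

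- Repeated-measures ANOVA, within or interaction term, f = d/2 = 0.375, three measurements, correlation 0. The noncentrality is f² × N × m = 0.375² × 26 × 3 = 10.97, and power is 0.827 at N = 26.
- One-sided pre-to-post test within one group of 13 at d = 0.75: power 0.817.

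So 26 can be reached, but the stated inputs do not determine it. Other repeated-measures settings tried at f = 0.375 (two or three measurements, correlation 0 to 0.7) give N from 10 to 50.

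**3. What 13 v 13 can detect.** The design compares active with vertex stimulation, so the natural yardstick is a two-sample t-test on change, two-sided 0.05. The degrees of freedom are 13 + 13 − 2 = 24, the critical value is 2.064, and the noncentrality is d × √(13/2) = 2.550 × d.

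| Between-group d | Origin | Noncentrality | Power |
|---|---|---|---|
| 1.145 | solved for 80% | 2.92 | 0.80 |
| 0.75 | 10.b value, read as the between-group difference | 1.91 | 0.45 |
| 0.5625 | assumed: three-quarters of 0.75 | 1.43 | 0.28 |
| 0.375 | assumed: half of 0.75 | 0.96 | 0.15 |

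The last two rows are illustrations. The documents give no effect for the outcomes without a pilot, so their power cannot be computed.

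**4. Sensitivity to the standardiser.** The stated inputs give 0.16/0.21 = 0.76, while the pilot's t(8) = 2.73 gives 2.73/√9 = 0.91 for a paired effect. At a between-group d of 0.91 power is about 0.61, still short of 0.80.

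**The case against.** The best defence is that 10.b already discloses much of this. For Experiments 2 and 4 it says plainly that there were no data and that 13 per group was copied from the parietal experiments, which is a matched size in all but name. The opening sentence can also be read as naming the kind of outcome used for sizing, FC rather than the memory scores. The plan acknowledges that cTBS may fail and builds in an early check. Borrowing the nearest available effect is common practice.

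Most of that is fair, and it narrows the point. It does not remove it. The 0.80 and the 26 are carried to each experiment in the calculation itself, so the striatal concession contradicts the claim and does not qualify it. The early check guards against a failed stimulation type but supplies no effect size. Borrowing is acceptable when stated as an assumption, and for Experiment 3 and tbFC it is not stated.

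The t-test on change is a yardstick chosen here. The plan names a repeated-measures ANOVA for sizing and voxelwise 3dLME for analysis, so the 1.15 SD figure belongs to that yardstick and not to the plan's model.

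Stronger readings are tempting, and the documents do not support them:

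- That exactly one of eight primary outcomes has a basis and the rest are passed over in silence. Eight is only a way of counting: section 9.a joins rsFC and tbFC with an and, section 2.a with an or, and tbFC comes from two tasks. The striatal gap is disclosed.
- That 10.b's sentence on the parietal group of Experiments 1 and 3 is wrong. It states a group size, which is true of both.
- That the investigators will read a null as proof that a network cannot be modulated. No section says so.

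**Conclusion.** The point holds as a mismatch between a general power claim and its evidence. The planning effect supports a statement about rsFC in Experiment 1 only. Experiments 2 and 4 lack a basis by the section's own admission. Experiment 3, and tbFC wherever it is primary, lack one without acknowledgement.

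A reader might infer that rsFC in Experiment 1 is therefore adequately powered. That does not follow: on the same active-versus-vertex comparison its power is about 45% at d = 0.75. Nor do the documents show that 26 is an arithmetic error, since unstated but standard settings reproduce it.

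The power figures assume 13 analysable participants per group, a two-sided 5% test, no multiplicity adjustment, and d = 0.75 read as a between-group difference in SDs of change. The pilot's d was a pre-to-post change without a control group, so that last reading is an assumption. That the pilot was resting-state rests on section 1.c, because 10.b does not say so.

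**What to change.** In section 10.b:

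1. Replace the opening claim that all experiments are powered. Limit the 0.80 statement, now extended to each experiment and the total of 104, to rsFC in Experiment 1.
2. State that 26 is a matched, not a powered, size for Experiments 2 to 4 and for all tbFC outcomes.
3. State for all experiments, including rsFC in Experiment 1, that 13 v 13 gives 80% power (two-sided 0.05, two-sample t-test on change) only for an active-versus-vertex difference of about 1.15 SD of change. Give about 45% power at d = 0.75 read as the between-group difference, with 28% and 15% at three-quarters and half of it, labelled as assumed illustrations.
4. Say that these outcomes will be reported as estimates with 95% CIs, and that a non-significant result will not be read as absence of modulation.

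The sentence on the group size of Experiments 1 and 3 can stay. The cost is wording and a less favourable stated power; enrolment and procedures do not change.

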#### Design

This study contains four between-subjects experiments and is a mixed inter-/intra subject design. Experiment 1 will use nominally excitatory stimulation targeting the hippocampal network to increase FC within the hippocampal network. We also expect to increase FC between the hippocampal and striatal networks, increased declarative memory, and a possible decrease in procedural, learning. Experiment 2 will use excitatory stimulation targeted to the striatal network. We expect this to cause stronger within-network FC in the striatal network, increased FC between the hippocampus and the striatal network and concomitant behavioral effects. Experiments 3 and 4 will be similar except that we will target nominally inhibitory stimulation to these networks and look for the inverse results. FC will be measured under resting and task-activated conditions and active rTMS will be compared to vertex sham.

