### b. Pilot Data

Pilot data from our laboratory show that enhancing the hippocampal network with rTMS via the PPC (Wang et al., 2014) is effective and replicable: Nine subjects tested showed significant FC increases between the hippocampus and regions that showed a group-level increase in FC with the hippocampus in Wang et al. (precuneus and medial occipital cortex;  $t(8) = 2.73, p < 0.05, d = 0.75$ ; Fig. 4). To show that these effects were specific to the hippocampus, we calculated FC changes between the dorsolateral prefrontal cortex and the same regions (i.e. precuneus and medial occipital cortex), and found no change from pre- to post-stimulation ( $p = 0.22$ ). Furthermore, the increase in hippocampus FC with the precuneus/medial occipital cortex were significantly greater than the change in global connectedness of the brain ( $t(8) = 2.62, p < 0.05, d = 0.58$ ), showing that these effects were network-specific.

These pilot data, however, also suggest rTMS targeted to the hippocampus and connected areas also affects the striatal network. Figure 4 shows statistically significant FC increases between the *caudate* and the precuneus/medial occipital cortex. Thus, in addition to increasing FC in the hippocampal network, rTMS also caused the striatum to be pulled into tighter association with the hippocampal network.

[figure not shown]

Figure 3. Hippocampal FC changes from Wang et al. (2014)  
Stimulation-dependent enhancement of hippocampal network overlaid on a template brain from Wang et al. (2014). The highlighted regions represent the areas that increased in FC with the hippocampus caused by PPC stimulation.

Structural equation modeling, which can be used to determine the direction of influence between network nodes, indicated a robust increase in connectivity from the striatum to the precuneus and medial occipital cortex after stimulation. This may explain why behavioral engagement of the hippocampal network interferes with procedural learning (Brown & Robertson, 2007; Poldrack et al., 2001). Based on these preliminary findings, we will guide rTMS to the hippocampal network and examine the effects on both the hippocampal-dependent memory system and the striatal memory system. We will also target the striatal network, and look for similar effects on the hippocampal network.

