### iv. rTMS

The parietal target in Experiments 1 and 3 will be the region of the left PPC with the greatest connectivity with the left hippocampus derived from the baseline resting-state fMRI session, (similar to Wang et al. 2014). The left PPC was chosen because of its dense connections with the hippocampus (Cavada & Goldman-Racic, 1989; Mesulam et al., 1977).

The target in Experiments 2 and 4 will be the M1 area of maximal connectivity with the right striatum. M1 has extensive projections to the striatum (Parent & Hazrati, 1995), and these regions are functionally connected at rest (Di Martino et al., 2008).

rTMS targets will be marked in the participant's anatomical MRI volume and located with a frameless stereotaxic system. If any experiment, for any reason, fails to produce useful individual targets, a literature-based location for the parietal cortex (Wang, et al., 2014) or motor cortex will be used as our location of stimulation. To reduce the influence of diurnal variations in the responsiveness to neuroplasticity protocols (Sale, Ridding, & Nordstrom, 2008), we will make every effort to test subjects during the same time of day.

*20-Hz Stimulation (facilitation)* will be delivered at 100% of the motor evoked potential threshold and 20-Hz in trains lasting 2 s for 20 min with 28 second rests in-between trains (similar to Wang et al., 2014).

*Continuous Theta-Burst Stimulation (cTBS; inhibition)* will be delivered at 80% of active motor threshold for 40 seconds (similar to Huang et al., 2005). cTBS consists of 50-Hz triplets separated by 200ms.

*Control stimulation.* As a negative control, rTMS will be delivered to the vertex with the same delivery parameter values and neuronavigation. Wang and colleagues (2014) used vertex stimulation as a control condition and found no significant effects on rsFC or behavior. In addition, there is no evidence that vertex stimulation causes other changes in rsFC (Jung et al., 2016).

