## **10. Statistical Analysis**

### **a. Analysis of data/ study outcomes**

Our primary aim is to examine stimulation-dependent changes in FC within the targeted network in each study. Secondary aims for this protocol will include all behavioral change data from the WPT-F and WPT-O and changes in FC to the non-targeted network, and between networks.

To calculate FC from resting-state scans, the Pearson correlation coefficients ( $r$ ) between time courses of BOLD activity in a seed region (i.e. hippocampus or striatum) will be calculated to determine the FC before and after rTMS stimulation. They will be Fisher-transformed to normalize  $r$ -values.

To calculate FC from task-based scans, the time series from a seed region will be inputted into a general linear model analysis as a regressor along with a regressor indicating when the task is occurring. For the WPT-F, this will include both the choice phase and the feedback phase during learning. For the WPT-O, this will include the observational trials and the retrieval trials. This analysis will be performed on each

individual to create a spatial map of beta values indicating the strength of the association between the seed and other regions during task performance.

*Statistical analysis for Experiments 1 and 3 (targeting the hippocampal network)*

iv. Preliminary Aims

Primary Aim 1

To confirm modulation of the hippocampal network, the average timeseries of the left hippocampal seed will be correlated with all other voxels with available data before and after stimulation. These data will be submitted to AFNI's 3dLME linear mixed effects function, which will be used to reveal potential areas of significant change in rsFC and tbFC.

v. Secondary Aims

Secondary Aims

Behavioral data will be submitted to a 3 x 2 x 2 ANOVA using timepoint (Pre-stimulation, post-stimulation, and follow-up), group (PPC vs. Vertex), and learning type (procedural and declarative) as factors. A significant interaction ( $p < 0.05$ ) between time, group, and learning type will confirm network-dependent modulation of each memory type.

To confirm changes in FC, a similar analysis will be performed as Primary Aim 1, except that the timeseries of the right striatum seed will be used instead of the hippocampal seed.

*Statistical Analysis for Experiments 2 and 4 (targeting the striatal network)*

i. Preliminary Aims

Preliminary Aim 1

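### The 80% power claimed for 13 per group is not supported for active versus vertex: the pilot's one-group pre-to-post effect gives about 60%, because comparing two groups' changes doubles the variance

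*Combined protocol and SAP*

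**What the plan says.** Section 10.b opens with "All experiments in this protocol are powered based on the primary outcome". It describes a G*Power repeated-measures ANOVA on FC change between the hippocampus and the precuneus/medial occipital cortex, with mean difference 0.16, pooled SD 0.21, d = 0.75, power 0.80 and alpha 0.05. It concludes that "26 right-handed healthy participants between 18 and 40 years of age will be needed (13 per group) for each experiment (104 total"). It does not give the sidedness, the number of measurements, the correlation between them, or whether the tested effect is within-group, between-group or an interaction.

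The source of the effect is section 1.b: "Nine subjects tested showed significant FC increases between the hippocampus and regions that showed a group-level increase", with t(8) = 2.73 and d = 0.75. No vertex group is reported there. The trial's own comparison is stated in the Précis under Design: "active rTMS will be compared to vertex sham". Section 4.a and Table 2 place active and vertex stimulation in separate groups of subjects.

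On the other experiments, 10.b says "There were no preliminary data to conduct a power analysis for stimulation involving the striatal network". The contingency text in section 4.d.iv begins "Because targeted inhibition of the hippocampal and striatal network with cTBS has not been demonstrated".

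**The concern.** The effect used for sizing answers a different question from the one the trial asks. The pilot shows whether FC changed within stimulated subjects. The trial asks whether it changed more under active than under vertex stimulation. With the same SD of change s and n per group, the variance of the estimate is s²/n for the first question and 2s²/n for the second.

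This is the only sample-size justification for four experiments and 104 people. If true power is well below 80%, a null result says less than the protocol implies. Because the G*Power settings are not given, a reader cannot tell which calculation produced 26.

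**Working it through.** **Inputs.** Mean change 0.16, SD 0.21, d = 0.75, alpha 0.05, 13 per group (10.b). Pilot n = 9, t(8) = 2.73 (1.b). Vertex change is set to 0, consistent with section 4.d.iv, which says an earlier study "used vertex stimulation as a control condition and found no significant effects on rsFC or behavior". The missing pilot control arm is therefore not the source of the shortfall. The SD of change is assumed equal in both groups.

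**Reproducing the plan's figure.** Several routes lead to 13 per group or 26, and the plan does not say which was used.
- One-group paired test, d = 0.75, one-sided 0.05: n = 13, power 81.7%.
- Group-by-time interaction with f = 0.75/4 = 0.1875, N = 26: power 82.7% with 2 measurements at correlation 0.8, or with 3 measurements at correlation 0.75.

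The interaction route does allow for two groups, but only at those correlations.

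**What the pilot implies.**
- Standardised change: dz = 2.73/√9 = 0.91.
- SD of change: 0.16/0.91 = 0.176.
- Pre-post correlation, from s² = 2 × 0.21² × (1 − ρ): ρ = 1 − 0.176²/(2 × 0.21²) ≈ 0.65.
- If 0.75 were the standardised change, the pilot would give t(8) = 0.75 × 3 = 2.25 (critical value 2.306, p = 0.055), which does not match 2.73. So 0.21 appears to be the SD of the FC values, not of the change.
- A correlation of 0.8 would imply t(8) of about 3.6, and 0.75 about 3.2.

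**Power for active versus vertex.** Two-sample t on change, 24 df, noncentrality d × √(13/2).

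| Standardised change | Two-sided | One-sided |
|---|---|---|
| 0.91 (from the pilot t) | 60.5% | 72.9% |
| 0.75 (as printed) | 45.1% | 58.4% |

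For comparison, a single group of 13 tested two-sided at 0.91 has 85.3%.

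**By correlation** (change 0.16, SD 0.21, two-sided):

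| Correlation | 0.5 | 0.65 | 0.75 | 0.78 |
|---|---|---|---|---|
| Power | 46% | 61% | 75% | 80% |

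One-sided, 80% needs a correlation of about 0.71.

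**Effect needed for 80%, two-sided.** A standardised difference of about 1.15, which is 1.15 × 0.176 = 0.20 FC units against the pilot's 0.16. At 0.91, 80% would take 20 per group.

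**Precision of the pilot.** With 8 df, the 95% CI for the SD of change is 0.119 to 0.337. At a change of 0.16 that puts power anywhere from about 91% to 21%.

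**ANCOVA on baseline**, two-sided, 23 df, residual SD 0.21 × √(1 − ρ²): 68.7% at ρ = 0.65 and 57.5% at ρ = 0.5. Simulation gives 67.3% and 55.7%.

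**Scope.** All these figures concern the one region pair used for sizing. Section 10.a plans a different analysis, in which the seed timeseries "will be correlated with all other voxels with available data before and after stimulation". No power is given for that voxelwise model.

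**The case against.** The strongest reply is that 26 can come from a proper group-by-time interaction, so the difficulty may be an unstated correlation rather than a forgotten control group. That is true as a possibility. The correlation it needs, 0.75 to 0.8, also lies within the pilot's uncertainty: the lower limit of 0.119 for the SD of change corresponds to a correlation of about 0.84. Section 1.a argues that FC is stable across sessions. But 10.b states no such assumption, and the pilot's point estimate is 0.65. An interval of 21% to 91% does not justify an unqualified 80%.

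A second reply is that better analyses exist. The aims are directional, and a one-sided ANCOVA at correlation 0.65 reaches about 80%. ANCOVA on the mean of the two post-stimulation scans reaches about 82% two-sided (simulated, equal correlations) if the effect is fully sustained at two weeks. Both stand as calculations. The first relies on a sidedness the plan never states. The second falls to 58% if the effect halves by two weeks, although section 1.a does cite earlier work reporting persistence. Neither analysis is in the plan.

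Third, the region pair serves only for sizing, and section 10.a contains no test on it. This is correct and limits what the 60% describes. The stated 80% is limited in the same way.

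Finally, 10.b openly says that striatal pilot data are lacking, and 4.d.iv admits the cTBS uncertainty. Experiment 3 at least targets the pilot's network, though with inhibitory stimulation. What remains there is the opening sentence of 10.b, which claims more than the text beneath it.

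**Conclusion.** The concern holds. On the pilot's own figures, 13 per group gives about 60% power for active versus vertex on the planning region pair, so an effect of pilot size would be missed about 4 times in 10 rather than 2 in 10. Reading the printed 0.75 as the standardised change makes it about 45%. One-sided testing gives 73% or 58%.

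This rests on no mean change under vertex, equal SD of change in both groups, a two-sided test for the headline figure, and a pre-post correlation near 0.65. The pilot of nine leaves the figure imprecise. How 26 was actually obtained cannot be determined from the document. For Experiments 2 to 4 the number is carried over, not powered.

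**What to change.** 1. Restate 10.b for the active-versus-vertex contrast on the hippocampus to precuneus/medial occipital pair. Give the contrast, sidedness, number of measurements and assumed correlation. Report two-sided power of about 60% (46% at correlation 0.5, 61% at 0.65, 75% at 0.75), and say that a pilot of nine leaves this uncertain.
2. Amend the opening sentence of 10.b to say that 26 in Experiments 2 to 4 is carried over from Experiment 1 and not powered.
3. Add an analysis of post-stimulation FC in that region pair by ANCOVA on baseline FC, with group as the contrast. Power rises to about 67% to 69% at correlation 0.65 (56% to 57% at 0.5). Two-sided, this does not by itself restore 80%, and 10.b should say so.

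The cost is two reworded statements and one model line, using scans already planned and no extra participants. The price is a less favourable stated power.
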